## 8.2.2 Adverse Events

### 8.2.2.1 Treatment-emergent Adverse Events (TEAEs)

TEAEs are defined as AEs with an onset date/time on or after the date/time of the first on study administration of TEGSEDI. Related TEAEs are TEAEs with a reported relationship of "Possible" or "Related". TEAEs with a missing relationship will also be counted as Related. Serious Adverse Events (SAEs) will be indicated as such in the eCRF and can be defined as treatment emergent, based on when the SAE initiated. AEs will be summarized using the safety set for the treatment period among both patients who develop a hypersensitivity reaction and those patients who do not develop a hypersensitivity reaction.

TEAEs will be summarized as follows:

- Overview of Treatment-emergent AEs
- Treatment-emergent AEs by System Organ Class and Preferred Term
- Treatment-emergent AEs by System Organ Class, Preferred Term and Severity
- Treatment-emergent AEs Related to TEGSEDI by System Organ Class and Preferred Term
- Treatment-emergent AEs Related to TEGSEDI by System Organ Class, Preferred Term and Severity
- Treatment-emergent Adverse Events of Special Interest (AESI) by System Organ Class and Preferred Term

 	
Title: Statistical Analysis Plan
 
Program Name: "A Phase 4 Safety Study Assessing the Adverse Events Occurring Within 24 Hours of TEGSEDI Administration in Patients with polyneuropathy of Hereditary Transthyretin-mediated Amyloidosis (hATTR-PN)"
 
Protocol #: TEG4004
 
[REDACTED]
 
Version: Final 2.0 Effective Date: 06 October 2023

--	---

- Treatment-emergent AESIs by System Organ Class, Preferred Term and Severity
- Treatment-emergent Serious AEs by System Organ Class and Preferred Term
- Treatment-emergent Serious AEs Related to TEGSEDI by System Organ Class and Preferred Term
- Treatment-emergent AEs leading to discontinuation of TEGSEDI by System Organ Class and Preferred Term

AEs will also be presented in data listings as follows:

- Listing of All Adverse Events
- Listing of Adverse Events Leading to Discontinuation
- Listing of Serious Adverse Events
- Listing of Adverse Events of Special Interest

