### 9.2.2.1.1. Screening

Written informed consent/assent for the study will be obtained prior to the performance of any study-related procedures including screening procedures. A 2-week period is provided for completing screening assessments and determining patient eligibility for the study. However, it is also possible for the screening visit and the Initial Treatment Visit (Month 0) to occur at the same time.

Patients must meet the required laboratory testing referenced in the applicable product label.

Medical history (including a retrospective chart review for relevant hATTR-PN disease history from the onset of the disease) and concomitant medications used within the past 12 months will be collected for each patient.

In addition, the following will be carried out at screening:

- Full Physical examination including height, weight and vital signs and examination of the following body systems: head, eyes, ear, nose throat (HEENT), cardiovascular, respiratory, lymphatic, gastrointestinal, musculoskeletal, dermatological, and neurological
- Urine pregnancy testing for women of childbearing potential

Demographics, including race & ethnicity, data will be collected for all enrolled patients.

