### **11.4.1. Serious Adverse Events**

In the interest of patient safety, and in order to fulfill regulatory requirements, all SAEs, AESIs, (regardless of their relationship to TEGSEDI) should be reported to the Sponsor or designee within 24 hours of the study center's first knowledge of the event. The collection of SAEs, AESIs, will begin after the patient signs the ICF and stop at the end of the patient's End of Study visit. When the investigator is reporting by telephone, it is important to speak to someone in person versus leaving a message. SAEs should be reported using an electronic SAE submission form whenever possible. In situations where the electronic SAE submission is unavailable, an Initial SAE Form should be completed, and a copy should be faxed or emailed to the Sponsor or designee. The SAE reporting instruction, including the fax number and email address can be found in the study safety form completion guidelines.

Detailed information should be actively sought and included on Follow-Up SAE Forms as soon as additional information becomes available. All SAEs will be followed until resolution. SAEs that remain ongoing past the patient's last protocol-specified visit will be evaluated by the investigator and Sponsor. If the investigator and Sponsor agree the patient's condition is unlikely to resolve, the investigator and Sponsor will determine the follow-up requirement.

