## 5.1 Patient Inclusion Criteria

To be eligible to enroll in this study, patients must meet the following eligibility criteria:

 	
Title: Statistical Analysis Plan
 
Program Name: "A Phase 4 Safety Study Assessing the Adverse Events Occurring Within 24 Hours of TEGSEDI Administration in Patients with polyneuropathy of Hereditary Transthyretin-mediated Amyloidosis (hATTR-PN)"
 
Protocol #: TEG4004
 
[REDACTED]
 
Version: Final 2.0 Effective Date: 06 October 2023

--	---

1. Satisfy one of the following:
  - a. US Patients: Adult patients ( $\geq 18$  years old) diagnosed with hATTR-PN and prescribed TEGSEDI according to the USPI (United States Prescribing Information)
  - b. Canadian Patients: Adult patients ( $\geq 18$  years old) diagnosed with stage 1 or stage 2 hATTR-PN and prescribed TEGSEDI according to the CPM (Canadian Product Monograph) (TEGSEDI CPM)
2. Must have given written informed consent for participation in this study
3. Must provide access to their previous medical records
4. Are about to initiate or have initiated treatment with TEGSEDI
5. Be willing to complete required testing and report any AEs and/or changes in medications
6. Satisfy one of the following:
  - a. Females: Non-pregnant and non-lactating; abstinent, or if engaged in sexual relations and of childbearing potential, patient is using an acceptable contraceptive method from time of signing the ICF (Informed consent form) until 13 weeks after the last dose of TEGSEDI administration
  - b. Males: Abstinent or if engaged in sexual relations with a female of childbearing potential, patient is utilizing an acceptable contraceptive method from the time of signing the ICF until 13 weeks after the last dose of TEGSEDI administration

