## 6 Schedule of Assessments

The study will consist of a Screening/Qualification period, a Treatment period and Post-Treatment Follow-up period as per Table 1 and Table 2.

The Screening/Qualification period is defined as the interval of time from the signing of informed consent until the first on-study dose of TEGSEDI.

The treatment period begins at the time of the first on study TEGSEDI administration and the end of treatment period is defined as follows:

- For patients who complete treatment with TEGSEDI on study, the last observation in the treatment period will be the 20-30 hour post-injection visit of the last administered TEGSEDI dose on study. If the time of the last TEGSEDI dose is missing, or the time of the assessment in question is missing, the assessment will be included in the treatment period if it occurred on the same day or one day subsequent to the last dose of TEGSEDI
- For patients who discontinue TEGSEDI or withdraw from the study and continue with TEGSEDI outside the study, the early termination (ET) visit will serve as the end of the treatment period

For patients who discontinue TEGSEDI, the post treatment follow-up period begins after the end of the treatment period, as defined above, and ends with the last available data collected per the clinical trial protocol. Data for the post-treatment follow-up period will be analyzed and summarized separately for patients who develop a hypersensitivity reaction.

	Title: Statistical Analysis Plan				
	Program Name: "A Phase 4 Safety Study Assessing the Adverse Events Occurring Within 24 Hours of TEGSEDI Administration in Patients with polyneuropathy of Hereditary Transthyretin-mediated Amyloidosis (hATTR-PN)"				
	Protocol #: TEG4004				
	[REDACTED]				
	Version: Final 2.0 Effective Date: 06 October 2023				

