**Table 1. Schedule of Assessments for Patients Who do not Develop a Hypersensitivity Reaction**

Study Periods	Screening 	Treatment Period				Post-Treatment Follow-up (Patients who discontinued TEGSEDI) 8-weeks (+/- 1 week) 
		Initial Treatment Visit (Month 0) and Every 4 months Visit (+/- 2 weeks) for 12 months		End of Study Visit		
Procedures and Testing	-2 to 0 weeks prior to first study injection	Pre-injection	Post injection 1-hour ± 15 mins 2-hour ± 15 mins 4-hour ± 30 mins 8-hour ± 30 mins 20-30 hours	Pre-injection	Post injection 1-hour ± 15 mins 2-hour ± 15 mins 4-hour ± 30 mins 8-hour ± 30 mins 20-30 hours	Early Termination Visit 
Informed Consent	X					
Demographics	X					
Medical History	X					
Full Physical Examination 	X					
Abbreviated Physical Examination 		X 		X		X X
Height	X					
Weight	X	X 		X		X X
Vital Signs	X	X	X	X	X	X X
Urine Pregnancy Testing	X 	X 		X 		X 
IgE, IgG, IgM		X	X	X	X	X

	Title: Statistical Analysis Plan
	Program Name: "A Phase 4 Safety Study Assessing the Adverse Events Occurring Within 24 Hours of TEGSEDI Administration in Patients with polyneuropathy of Hereditary Transthyretin-mediated Amyloidosis (hATTR-PN)"
	Protocol #: TEG4004
	[REDACTED]
	Version: Final 2.0 Effective Date: 06 October 2023

Inflammatory Markers		X	X	X	X	X	
Samples for Possible Future Testing		X	X	X	X	X	X
ADA		X 		X		X 	
Adverse Events Post Injection at Study Visit			X		X		
Concomitant Medications	X	X		X		X	X

1. The Screening visit and the Month 0 visit can occur on the same day.
2. The Physical Examination and Weight does not need to be completed at the Month 0 study visit if they were performed during Screening.
3. If the patient withdraws from the study, the patient should return for an ET visit within 2 weeks after the decision to withdraw from the study. If the patient discontinues TEGSEDI, they should have an ET visit within 2 weeks of the decision to end treatment and one follow-up visit 8-weeks ( $\pm$  1 week) after their last dose of TEGSEDI. If the ET and the 8 week follow up visit are within 2 weeks of each other, the assessments can be combined.
4. Urine pregnancy testing is only for women of childbearing potential as defined in the protocol.
5. The baseline ADA sample is only drawn at the Month 0 visit.

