### 8.2.5 TEGSEDI Administration and Exposure

TEGSEDI administration will be summarized using the safety set by both individual study visit and an overall study drug administration using a derived algorithm. Each visit will summarize the injection location, dose (mg), volume, number of patients having any hypersensitivity and

 	
Title: Statistical Analysis Plan
 
Program Name: "A Phase 4 Safety Study Assessing the Adverse Events Occurring Within 24 Hours of TEGSEDI Administration in Patients with polyneuropathy of Hereditary Transthyretin-mediated Amyloidosis (hATTR-PN)"
 
Protocol #: TEG4004
 
[REDACTED]
 
Version: Final 2.0 Effective Date: 06 October 2023

--	---

the number of patients taking any preventive measures prior to administration as recorded on the Dosing at Visit eCRF. For the overall analysis, the first on-site visit injection will initiate the start of TEGSEDI for this protocol. It will be assumed that the dose at a specific visit will be applied weekly from each specific visit until the subsequent visit, unless captured in the injection dosing log. Total exposure will be estimated using the number of doses, duration of exposure and dose intensity as mg/week and will use both the visit date as recorded for the on-site injection in combination with the dosing log form to calculate any changes.

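### In patients already taking TEGSEDI at consent, adverse events on drug between consent and the Month 0 injection reach no AE summary table

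*Combined protocol and SAP*

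**What the plan says.** - **Start of treatment emergence.** SAP 8.2.2.1: "TEAEs are defined as AEs with an onset date/time on or after the date/time of the first on study administration of TEGSEDI". For exposure, SAP 8.2.5 says that "the first on-site visit injection will initiate the start of TEGSEDI for this protocol".
- **Study periods.** SAP 6 uses the same anchor: "The treatment period begins at the time of the first on study TEGSEDI administration". Screening is "defined as the interval of time from the signing of informed consent until the first on-study dose of TEGSEDI". SAP 8.2.2.1 limits its AE summaries to the treatment period.
- **Who may enter.** SAP 5.1, criterion 4: "Are about to initiate or have initiated treatment with TEGSEDI". Protocol v2.0, section 9.2.1, also admits treated patients but caps prior doses at 9. Note (a) to SAP 5.1 admits patients who stopped TEGSEDI and later restart.
- **Length of screening.** Protocol 9.2.2.1.1: "A 2-week period is provided for completing screening assessments and determining patient eligibility for the study". The screening column of SAP Table 1 runs from minus "2 to 0 weeks prior to first study injection", and a footnote lets both visits fall on one day.
- **Collection of events.** Protocol 11.4.1: "The collection of SAEs, AESIs, will begin after the patient signs the ICF". Section 11.4.2 sets the same start for non-serious AEs.
- **Outputs.** All general AE tables in SAP 8.2.2.1, and all AE tables in the annual progress report (SAP 9), are restricted to treatment-emergent events. Protocol 9.6.4 plans incidence of all AEs by SOC and PT, together with narratives of deaths, discontinuations, SAEs, pregnancies and AESIs.

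**The concern.** In a drug-naive patient, the time between consent and the first on-study dose is off drug, and leaving it out of treatment-emergent tables is correct. In a patient already injecting weekly, the same interval is exposed time. An event then comes after consent, so protocol 11.4 does not let it go to medical history unless the condition was already present. It also comes before Month 0, so the SAP does not call it treatment-emergent. It falls between the two categories.

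At stake is whether the general safety tables, and the annual reports built from them, count every on-drug event that the study collects. Protocol 9.8 already warns that early AESIs may be under-represented because some patients start treatment before enrolling. The TEAE rule adds a further, smaller omission of the same kind, this time among events that were observed.

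**Working it through.** The plan states no figure for this rule, so there is none to reproduce. Its only sizing figure (75 patients, 95% probability, 4% incidence) checks out, 1 − 0.96^75 = 0.953, but the point does not depend on it.

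**Step 1. Follow one event through the rules.** Take a patient on weekly TEGSEDI who consents 14 days before Month 0 and has an SAE on day 7.

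| Output | Rule | Event included? |
|---|---|---|
| Medical history | Present before consent (protocol 11.4) | No |
| General TEAE, SAE and AESI tables | Onset from first on-study dose; treatment period only (SAP 8.2.2.1, SAP 6) | No |
| 24-hour AE tables | Tied to injections at study visits (SAP 3, 8.2.2.2) | No, and not meant to be |
| Annual report AE tables | Treatment-emergent (SAP 9) | No |
| Table of all AEs | Planned in protocol 9.6.4; absent from the SAP's list | No such table |
| AE and SAE listings | Not limited to TEAEs; run on the safety set (SAP 8.1, 8.2.2.1) | Yes, if in the safety set |
| SAE and AESI narratives | Protocol 9.6.4, no treatment-emergent limit | Yes |

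**Step 2. Size of the gap.** Inputs: gap w = 0 to 2 weeks (SAP Table 1), weekly dosing (protocol abstract), follow-up of 52 weeks (12 months) or 104 weeks (24 months). Share of on-drug time from consent = w / (w + follow-up).

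- w = 0: 0%
- w = 1: 1/53 = 1.9% (12 months); 1/105 = 1.0% (24 months)
- w = 2: 2/54 = 3.7% (12 months); 2/106 = 1.9% (24 months)

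At most about 2 weekly doses per already-treated patient fall in the gap.

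**Step 3. Number of patients (illustration only).** The documents give neither the share s already on drug at consent nor the weekly risk r of an AE; both are assumed here. Expected patients with at least one on-drug AE in the gap = 75 × s × (1 − (1 − r)^w). With w = 2:

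- s = 25%, r = 1%: 18.75 × 0.0199 = 0.37
- s = 50%, r = 4%: 37.5 × 0.0784 = 2.94
- s = 100%, r = 10%: 75 × 0.19 = 14.25

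The range is about 0.4 to 14 patients if everyone uses the full 2 weeks, and 0 if every screening visit is on the Month 0 day.

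**The case against.** The strongest reply is that the study's endpoints are untouched. They concern the 24 hours after injections at study visits, and no such injection precedes Month 0. This stands. A reader might infer that the main AE incidence is biased by the TEAE rule; the documents give no support for that.

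A reader might also infer that these events disappear altogether, above all when one stops TEGSEDI before Month 0. That goes too far. The listings in SAP 8.2.2.1 are not restricted to TEAEs, protocol 9.6.4 requires narratives for discontinuations, SAEs and AESIs, and protocol 11.4.1 has SAEs and AESIs reported to the sponsor within 24 hours. SAP 8.1 defines the safety set by a dose received during enrolment and does not require it to be on site, so on its plain words a home dose after consent qualifies. Only if the on-site anchor of SAP 8.2.5 were carried into that definition would such a patient leave the listings too. That ambiguity is worth closing, but the loss is not shown.

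Third, the supplied protocol is v2.0, while the SAP implements v3.0. Collection from consent is v2.0 text, and the SAP schedules as supplied lack v2.0's row for AEs since the last visit. This stands as a caveat on the premise. If v2.0 is relied on for collection, its narratives count as well.

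Finally, *first on study administration* could be read as any dose after consent, which would remove the problem. SAP 8.2.5 and the screening column of SAP Table 1 point to the on-site injection instead.

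**Conclusion.** The point holds, within limits. For a patient on TEGSEDI at consent whose screening and Month 0 fall on different days, on-drug AEs in the gap are left out of every AE, SAE and AESI summary table, although protocol v2.0 collects them and plans incidence of all AEs. The omission covers at most 3.7% of that patient's on-drug time over 12 months (1.9% over 24). It is zero for same-day screening and for patients who first start TEGSEDI at Month 0. Listings and narratives remain as a partial safeguard, and the 24-hour analyses do not change.

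This rests on three assumptions: that the on-study dose in SAP 8.2.2.1 is the on-site Month 0 injection, that the 2-week screening limit is kept, and that protocol v3.0 still collects AEs from consent. The number of patients affected cannot be derived from the documents.

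**What to change.** 1. Keep Month 0 as the anchor for TEAEs, the treatment period, exposure and the 24-hour analyses. Moving only the TEAE flag would put events in the tables from weeks that the treatment period and exposure exclude. Starting TEAEs at the later of consent and the first-ever dose would also wrongly count off-drug events in patients who stopped and have not yet restarted.
2. Add to SAP 8.2.2.1 and the annual report a separate summary, by SOC and PT and with SAEs and AESIs identified, of AEs with onset from consent to the Month 0 injection. It covers patients on TEGSEDI at consent and, from that dose on, patients who take a dose within the interval. Patients who have stopped and not yet restarted are not counted as on drug.
3. State in SAP 8.1 that a TEGSEDI dose taken at home after consent places the patient in the safety set, so that the listings include someone who stops before Month 0.

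The cost is one extra table and a few sentences in the SAP. It also requires TEGSEDI status and dose dates between consent and Month 0 in the eCRF. Protocol 9.2.4.7 records patient-reported compliance between study visits, but no section shows that dated doses before Month 0 are captured, so this should be confirmed first.

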### 8.2.2.2 Adverse Events Occurring Within 24 hours of TEGSEDI Administration

AEs occurring within 24 hours of administration of TEGSEDI are defined as all AEs with an onset date/time no longer than the 24-hour planned timepoint using a window interval from 20 to 30 hours after the date/time of the injection. For AEs with missing time of onset, AEs occurring within 24 hours of TEGSEDI administration are defined as AEs with an onset date of the same day as the TEGSEDI administration or the subsequent day. This rule will also be applied for missing time of administration of TEGSEDI.

The incidence of AEs occurring within 24 hours post TEGSEDI administration will be summarized at each visit and overall using counts and percentages in the evaluable set. The incidence will be reported with 95% confidence intervals (CIs). Additionally, a summary of AEs occurring within 24 hours post TEGSEDI administration will be displayed by SOC and PT and will be summarized at each visit and overall.

The denominator for the calculation of the percentages by visit will be the number of patients who received a TEGSEDI administration for the specific visit. The denominator for the calculation of the percentages for the overall occurrence of AEs in any visit will be the number of patients in the evaluable set. These denominators will also be presented in the table.

The time from the injection of TEGSEDI until the occurrence of the first AE will be summarized by each visit and overall using descriptive statistics for continuous variables. The time (hours) will be calculated as:

(Onset date/time of the AE – injection date/time of TEGSEDI)/3600

Time from injection of TEGSEDI until the onset of the AE will only be summarized for the AEs with available time for the onset of the AE and available time of TEGSEDI injection. Where time is not available, the AE will be included in the incidence count but will not be included in the summary of time to onset.

The duration of AEs occurring within 24 hours of TEGSEDI administration (in hours) will be calculated as:

- $(\text{Date/time of resolution} - \text{date/time of onset})/3600$

Duration of the AEs will only be calculated for AEs with an outcome of "Recovered" or "Recovered with sequelae" for which date/time for onset and resolution is available.

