#### 9.1.2. Study Visits for all Patients While Being Treated With TEGSEDI

During the study visits, a scheduled dose of TEGSEDI will be injected and the patients will be monitored at 1, 2, 4, and 8 hours post injection for AEs assessments, changes in vital signs and laboratory testing. The patient will return to the clinic 20-30 hours post injection for a further assessment of AEs, vital signs and laboratory testing. In addition to these study visits, the patient will be monitored according to the USPI or CPM. Additional blood samples will be drawn and stored for possible non-genetic testing in this study.

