### 3 Study Objectives

The objective of the study is to characterize adverse events (AEs) occurring within 24 hours of TEGSEDI administration in adult patients with hATTR-PN and in individual patients with respect to time course of AE onset, vital sign changes, preventive measures, treatment required, risk factors, and subsequent adverse outcomes.

The endpoints of the study are AEs occurring within the first 24 hours of TEGSEDI administration at study visits, changes in vital signs and cytokines and inflammatory markers 24-hour post-injection with additional assessments of:

- Preventive measures used prior to the injection
- Treatment of AEs post 24 hour injection of TEVESDI at study visits
- Identification of risk factors for AEs occurring within the first 24 hours of TEVESDI administration at study visits
- Correlation of subsequent adverse outcomes

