## 7 Outcome Variables

Outcomes are measured by reported AEs, changes in vital signs and cytokines/inflammatory markers over a 24 hour interval post-injection of TEGSEDI.

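### The SAP counts adverse events within 24 hours using the 20-30 h return-visit window, so a timed event at 24-30 h falls under a 24 h label

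*Combined protocol and SAP*

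**What the plan says.** SAP section 3 gives the endpoint as "AEs occurring within the first 24 hours of TEGSEDI administration at study visits". SAP section 7 describes outcomes measured "over a 24 hour interval post-injection of TEGSEDI".

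SAP 8.2.2.2 turns this into a counting rule. AEs within 24 hours are those "defined as all AEs with an onset date/time no longer than the 24-hour planned timepoint using a window interval from 20 to 30 hours", timed from the injection date and time. If the onset time or the injection time is missing, the rule counts "AEs with an onset date of the same day as the TEGSEDI administration or the subsequent day". For such an event, "the AE will be included in the incidence count but will not be included in the summary of time to onset".

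The 20-30 h range comes from the visit schedule. Protocol 9.1.2 states: "The patient will return to the clinic 20-30 hours post injection for a further assessment of AEs, vital signs and laboratory testing". SAP section 6 uses the same range to close the treatment period for patients who complete treatment: "the last observation in the treatment period will be the 20-30 hour post-injection visit of the last administered TEGSEDI dose on study". Tables 1 and 2 in that section list post-injection assessments at 1, 2, 4 and 8 hours and at 20-30 hours. They name no separate 24-hour point.

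**The concern.** A visit window suits vital signs and blood samples, because they are taken at the visit. AE onset has its own date and time, and SAP 8.2.2.2 already uses both in its time-to-onset formula. There is no need to borrow a scheduling tolerance to decide whether an event began in the first 24 hours.

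The study is descriptive, and this flag defines its central count. It feeds:

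- the incidence by visit and overall with 95% confidence intervals, the tables by system organ class and preferred term, and the time-to-onset and duration summaries (SAP 8.2.2.2);
- the incidence with and without preventive measures, and duration with and without treatment (same section);
- the split of vital signs and of cytokines and inflammatory markers by presence or absence of an AE (SAP 8.2.3 and 8.2.4);
- the 24-hour tables in the annual progress reports (SAP section 9).

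If the limit is 30 h, each of these carries a 24 h label over a period that is up to 25% longer (30/24 = 1.25).

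**Working it through.** **The plan's own figure.** Protocol 9.4 says that 75 patients give 95% probability of detecting an AE that occurs in 4% of patients. The probability of at least one event is 1 − 0.96^75 = 0.953, so the figure is reproduced. It does not depend on the window and is not in question.

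**Which limit the rule implies.** The definition names a planned 24-hour timepoint, attaches a 20-30 h window, and anchors that window to the injection time. It does not mention the actual time of the return visit. An upper limit expressed through that window most naturally falls at 30 h. Three cases show the effect for AEs with known times:

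| Onset after injection | Section 3 endpoint | 8.2.2.2, limit at 30 h |
|---|---|---|
| 22 h | counted | counted |
| 28 h | not counted | counted |
| 31 h | not counted | not counted |

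Only onset after 24 h and up to 30 h is classified differently, and always towards inclusion.

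**Size.** The documents give neither an AE incidence nor an onset pattern. The inputs here are assumptions: 75 patients dosed at a visit, all AEs timed, and 5% true incidence in 24 h.

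*Constant hazard.*
- r = −ln(0.95)/24 = 0.002137 per hour; p(h) = 1 − exp(−r·h).
- p(24) = 5.0%, or 3.75 of 75 patients.
- p(30) = 6.2%, or 4.66 of 75 patients.
- Increase: 1.2 points, about 0.9 patients.

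*Early clustering.* Onset is exponential with median m hours, scaled so that the 24 h incidence stays at 5%.
- F(t) = 1 − 2^(−t/m); Λ = −ln(0.95)/F(24); p(30) = 1 − exp(−Λ·F(30)).
- m = 8 h: F(24) = 0.875, F(30) = 0.926, p(30) = 5.28%. Increase: 0.28 points, about 0.2 patients.
- m = 4 h: F(24) = 0.984, F(30) = 0.994, p(30) = 5.05%. Increase: 0.05 points, about 0.04 patients.

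*Other incidences.* Under constant hazard, p(30) = 1 − (1 − p(24))^1.25:

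| Assumed 24 h incidence | At 30 h | Extra patients of 75 |
|---|---|---|
| 4% | 5.0% | 0.7 |
| 5% | 6.2% | 0.9 |
| 10% | 12.3% | 1.8 |
| 20% | 24.3% | 3.3 |

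Constant hazard is the less favourable of the two onset patterns tried. Clustering soon after the injection shrinks the increase.

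**Against the precision of the estimate.** By the Clopper-Pearson method named in SAP section 8, 4/75 is 5.3% (1.5% to 13.1%) and 5/75 is 6.7% (2.2% to 14.9%). One extra patient is small against either interval.

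**The case against.** The strongest reply is that the rule is pre-specified and open. The SAP states its definition and its window, and the supplied protocol (v2.0) speaks only of one day, with no hour limit. Over-inclusion is the cautious direction for a safety count. No hypothesis is tested, so no error rate is affected. The SAP also plans a listing of all AEs and a time-to-first-AE summary with its maximum. All of this stands, and it limits the importance of the point. It does not remove the mismatch, because section 3 of the same SAP says first 24 hours. The maximum can show that a timed first AE came after 24 h, but not how many patients were counted for that reason.

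A reader might infer four stronger points that the documents do not support.

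- *The rule drops early events.* If the cut-off were each patient's actual visit time, an AE at 22 h would be lost for a patient seen at 20 h. The text ties the window to the injection and never mentions actual visit time, so this reading is weak. The SAP schedules list only "Adverse Events Post Injection at Study Visit", so it is also not established that such an event would be collected after an early visit.
- *Section 7 sets a strict 24 h limit.* It also covers vital signs and cytokines, whose last planned measurement is at 20-30 h. There, 24 hours may be a nominal label. Section 3 is the firmer support.
- *The rule for untimed AEs is a defect.* It is a defensible inclusive convention, and the SAP says that such events enter the incidence but not time to onset.
- *AEs before the injection are counted.* SAP 8.2.2.2 describes the incidence as following administration, and the schedules collect post-injection events, so this is at most a corner case.

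**Conclusion.** The point holds as a mismatch between the endpoint and its counting rule. Under the natural reading of SAP 8.2.2.2, a timed AE with onset after 24 h and up to 30 h is counted as within 24 hours, in the main incidence and in every output that uses the flag.

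The effect is probably small: at an assumed 5% incidence, from almost nothing up to about 0.9 of 75 patients, depending on how early onset clusters. A higher incidence would give more. The argument for a change is therefore a correctly labelled and reproducible central count, and the documents give no basis for claiming a large bias.

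The SAP is written to protocol v3.0, and its table layouts are in Appendix B. Neither was available, and either might fix the limit or label the tables. The wording of 8.2.2.2 would still need to agree with section 3.

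**What to change.** - For AEs with known onset and injection times, define the 24 h incidence as 0 ≤ (onset time − that visit's injection time) ≤ 24 h.
- Show onset after 24 h and up to 30 h in a separate row, followed by the inclusive total.
- State which flag forms the AE and no-AE groups in SAP 8.2.3 and 8.2.4. The inclusive flag is acceptable there if labelled, because the measurements themselves run to 30 h.
- Keep the same-day or next-day rule for untimed AEs as it stands.

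The cost is a change of SAP wording and one extra table row. No new data are needed, because the time-to-onset formula already uses both times. The 24 h figure may be slightly lower than the inclusive total, which remains on display, so no late event is hidden.
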